7.4.5 Blinding of the Test Article

Not a blinded study

7.4.6 Receiving, Storage, Dispensing and Return

7.4.6.1 Receipt of Test Article

The 2% lidocaine jelly is dispensed as a single dose unit (syringe prefilled with 6 mL of medication) and be obtained by and stored in the inpatient Pharmacy according to their standard procedures.

7.4.6.2 Storage

The 2% lidocaine jelly will be obtained by and stored in the inpatient Pharmacy according to their standard procedures

7.4.6.3 Preparation and Dispensing

The 2% lidocaine jelly is dispensed as a single dose unit (syringe prefilled with 6 mL of medication) and will be obtained from the inpatient Pharmacy according to their standard procedures. The investigator will squirt 1ml of this medication onto the cotton tipped plastic applicator immediately prior to use.

7.4.6.4 Return or Destruction of the Test Article

These are single dose dispensers and unused drug will be discarded as per hospital policy

7.4.6.5 Prior and Concomitant Therapy

Not applicable

8.0 Subject Numbers and Statistical Plan

8.1 Number of Subjects

Thirty

8.2 Sample size determination

Convenience Sample: This is a pilot study and this number was selected to complete this study over one year. The data collected will be used for a formal sample size calculation, if appropriate, to plan a larger study.

8.3 Statistical methods

It would be mainly descriptive statistics looking at time to onset of pain relief, the duration of pain relief, failure of the procedure to relieve PDPH, description and frequency of any side effects at one week and 1 month.

The number of patients who do not get any or inadequate pain relief and if they need an epidural blood patch, it will be considered a failure of this technique.

9.0 Confidentiality, Privacy and Data Management

See the Research Data Review Form

10.0 Data and Safety Monitoring Plan

10.1 Periodic evaluation of data

Every patient will be reviewed for any harmful effects due to the SP ganglion block

10.2 Data that are reviewed

Refer to above

10.3 Method of collection of safety information

Safety information will be collected by interview of subjects at the time of intervention. Afterwards, safety information will be collected by telephone interview.

10.4 Frequency of data collection

Data will be collected at the time of intervention, Day 1, 2 and 7 post-procedural days and 1 month following intervention.

10.6 Frequency of review of cumulative data

Data will be reviewed after every 5 patients have undergone intervention.

10.7 Statistical tests

It would be mainly descriptive statistics looking at time to onset of pain relief, the quantum of pain relief, the duration of pain relief, failure of the procedure to relieve PDPH, description and frequency of any side effects at one week and 1 month.

10.8 Suspension of research

Unexpected problems such as consistent trend of worsening morbidity in the immediate or long-term setting of study intervention

11.0 Risks

Insertion of the cotton swab stick into the nostril can cause:

- mild pressure or a feeling like you have to sneeze
- brief mild discomfort or irritation in the nose
- brief or quick burning sensation
- bad taste in your mouth as some of the lidocaine may drip down into your mouth
- tearing and a brief temperature change
- temporary numbness in the throat related to a small amount of the lidocaine dripping into your mouth
(This numbness should not last more than a few hours. During this time, it is safest if you avoid eating or drinking anything to avoid the risk of choking)
- nasal bleeding or infection have been reported, in some cases may be severe bleeding
- rarely, a temporary increase in pain has been reported

You may have temporary or no relief from procedure

There is a possibility of an allergic reaction to lidocaine.

Loss of confidentiality

Nursing mothers: The amount of lidocaine that may be absorbed into the blood stream, from this procedure, and excreted in the breast milk is minimal, and studies have shown that if nursing mothers undergoes even dental treatment with lidocaine, it is safe to continue breast-feeding.⁶

From the Glydo package insert:

Lidocaine is not contraindicated during labor and delivery. Lidocaine is secreted in human milk. Although, safety and effectiveness of lidocaine in pediatric patients have not been established, a study of 19 premature neonates where about 7mg/kg of lidocaine was used to lubricate intranasal tubes, the plasma levels of lidocaine was acceptable.

However, if our subject is breast-feeding then we will advise her NOT to feed her baby for next 4h and to express the breast milk and discard.

12.0 Potential Benefits to Subjects and Others

12.1 Potential Benefits to Subjects

The SP ganglion block may reduce the PDPH

12.2 Potential Benefits to Others

If found effective, this could provide a less invasive alternative management for PDPH

13.0 Sharing Results with Subjects

Not applicable

14.0 Subject Stipend (Compensation) and/or Travel Reimbursements

Not applicable

15.0 Economic Burden to Subjects

15.1 Costs

The research will pay for the costs of the medication used for the SP ganglion block (Lidocaine 2%) and its administration.

15.2 Compensation for research-related injury

It is the policy of the institution to provide neither financial compensation nor free medical treatment for research-related injury. In the event of injury resulting from this research, medical treatment is available but will be provided at the usual charge. Costs for the treatment of research-related injuries will be charged to subjects or their insurance carriers.

16.0 Resources Available

16.1 Facilities and locations

Penn State Health Milton S. Hershey Medical Center, Hershey PA

16.2 Feasibility of recruiting the required number of subjects

Over a 1-year period, the study would have access to approximately 50 potential subjects.

16.3 PI Time devoted to conducting the research

The PI is allotted academic time for research and other scholarly activities

16.4 Availability of medical or psychological resources

All resources and facilities of HMC are available to subjects on study.

16.5 Process for informing Study Team

Each member of the study will complete CITI training. The procedure will be done by or under supervision of the PI. Additionally research team will meet monthly to review procedures and protocols.

17.0 Other Approvals

17.1 Other Approvals from External Entities

Not applicable

17.2 Internal PSU Committee Approvals

Check all that apply:

- Anatomic Pathology – Hershey only – Research involves the collection of tissues or use of pathologic specimens. Upload a copy of HRP-902 - Human Tissue For Research Form on the “Supporting Documents” page in CATS IRB. This form is available in the CATS IRB Library.
- Animal Care and Use – All campuses – Human research involves animals and humans or the use of human tissues in animals
- Biosafety – All campuses – Research involves biohazardous materials (human biological specimens in a PSU research lab, biological toxins, carcinogens, infectious agents, recombinant viruses or DNA or gene therapy).
- Clinical Laboratories – Hershey only – Collection, processing and/or storage of extra tubes of body fluid specimens for research purposes by the Clinical Laboratories; and/or use of body fluids that had been collected for clinical purposes, but are no longer needed for clinical use. Upload a copy of HRP-901 - Human Body Fluids for Research Form on the “Supporting Documents” page in CATS IRB. This form is available in the CATS IRB Library.
- Clinical Research Center (CRC) Advisory Committee– All campuses – Research involves the use of CRC services in any way.
- Conflict of Interest Review – All campuses – Research has one or more of study team members indicated as having a financial interest.
- Radiation Safety – Hershey only – Research involves research-related radiation procedures. All research involving radiation procedures (standard of care and/or research-related) must upload a copy of HRP-903 - Radiation Review Form on the “Supporting Documents” page in CATS IRB. This form is available in the CATS IRB Library.
- IND/IDE Audit – All campuses – Research in which the PSU researcher holds the IND or IDE or intends to hold the IND or IDE.
- Scientific Review – Hershey only – All investigator-written research studies requiring review by the convened IRB must provide documentation of scientific review with the IRB submission. The scientific review requirement may be fulfilled by one of the following: (1) external peer-review process; (2) department/institute scientific review committee; or (3) scientific review by the Clinical Research Center Advisory committee. NOTE: Review by the Penn State Hershey Cancer Institute Scientific Review Committee is required if the study involves cancer prevention studies or cancer patients, records and/or tissues. For more information about this requirement see the IRB website at:
<http://www.pennstatehershey.org/web/irb/home/resources/investigator>

18.0 Multi-Site Research

Not applicable

19.0 Adverse Event Reporting

19.1 Adverse Event Definitions

For drug studies, incorporate the following definitions into the below responses, as written:	
Adverse event	Any untoward medical occurrence associated with the use of the drug in humans, whether or not considered drug related

Adverse reaction	Any adverse event caused by a drug
Suspected adverse reaction	Any adverse event for which there is a reasonable possibility that the drug caused the adverse event. Suspected adverse reaction implies a lesser degree of certainty about causality than “adverse reaction”. 
 • Reasonable possibility. For the purpose of IND safety reporting, “reasonable possibility” means there is evidence to suggest a causal relationship between the drug and the adverse event.
Serious adverse event or Serious suspected adverse reaction	Serious adverse event or Serious suspected adverse reaction: An adverse event or suspected adverse reaction that in the view of either the investigator or sponsor, it results in any of the following outcomes: Death, a life-threatening adverse event, inpatient hospitalization or prolongation of existing hospitalization, a persistent or significant incapacity or substantial disruption of the ability to conduct normal life functions, or a congenital anomaly/birth defect. Important medical events that may not result in death, be life-threatening, or require hospitalization may be considered serious when, based upon appropriate medical judgment, they may jeopardize the patient or subject and may require medical or surgical intervention to prevent one of the outcomes listed in this definition.
Life-threatening adverse event or life-threatening suspected adverse reaction	An adverse event or suspected adverse reaction is considered “life-threatening” if, in the view of either the Investigator (i.e., the study site principal investigator) or Sponsor, its occurrence places the patient or research subject at immediate risk of death. It does not include an adverse event or suspected adverse reaction that had it occurred in a more severe form, might have caused death.
Unexpected adverse event or Unexpected suspected adverse reaction.	An adverse event or suspected adverse reaction is considered “unexpected” if it is not listed in the investigator brochure, general investigational plan, clinical protocol, or elsewhere in the current IND application; or is not listed at the specificity or severity that has been previously observed and/or specified.

For device studies, incorporate the following definitions into the below responses, as written:	
Unanticipated adverse device effect	Any serious adverse effect on health or safety or any life-threatening problem or death caused by, or associated with, a device, if that effect, problem, or death was not previously identified in nature, severity, or degree of incidence in the investigational plan or IDE application (including a supplementary plan or application), or any other unanticipated serious problem associated with a device that relates to the rights, safety, or welfare of subjects.

19.2 Recording of Adverse Events

Research subjects will be routinely questioned about adverse events during the procedure and in the follow-up phone calls.

All adverse events (serious or non-serious) and abnormal test findings observed or reported to study team believed to be associated with the study drug(s) or device(s) will be followed until the event (or its sequelae) or the abnormal test finding resolves or stabilizes at a level acceptable to the investigator.

An abnormal test finding will be classified as an adverse event if one or more of the following criteria are met:

- The test finding is accompanied by clinical symptoms

- The test finding necessitates additional diagnostic evaluation(s) or medical/surgical intervention; including significant additional concomitant drug treatment or other therapy
NOTE: Simply repeating a test finding, in the absence of any of the other listed criteria, does not constitute an adverse event.
- The test finding leads to a change in study drug dosing or discontinuation of subject participation in the clinical research study
- The test finding is considered an adverse event by the investigator.

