1.3 Secondary Study Endpoints

1. To monitor any complications due to SP ganglion block
2. To measure patient satisfaction
3. To monitor any residual effects at 1 months after the SP block

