2.0 Background

2.1 Scientific Background and Gaps

Lumbar puncture is a commonly performed diagnostic procedure in medicine and also for anesthesia. Inadvertent dural puncture can occur during epidural anesthesia and placement of an epidural catheter. Headache after a dural puncture is not uncommon and is excruciatingly painful. Most often it is self-limited and the pain subsides within 1-2 weeks. However, if left untreated, it can lead to considerable morbidity including chronic neck and back pain, subdural hematoma, seizures and even death.

According to the Headache Classification Committee of the International Headache Society, headache after lumbar puncture is defined as “bilateral headaches that develop within 7 days after a lumbar puncture and disappears within 14 days. The headache worsens within 15 min of resuming the upright position, disappears or improves within 30 min of resuming the recumbent position”. This definition helps to avoid confusion with migraine or simple headache after lumbar puncture.

Currently, the standard practice to manage this headache is to do an epidural ‘blood-patch’, wherein an anesthesiologist performs an epidural puncture in the lumbar spine after numbing the skin and subcutaneous tissue with 2-3 ml of 2% lidocaine and injects 20-30ml of the patient’s blood into the epidural space. The intention is for the blood to clot and seal the dural puncture. This is effective about 90% of the time and can be repeated if it fails. Introduction of infection, arachnoiditis, or another inadvertent dural puncture are possible complications. Some patients opt not to have the epidural blood patch for fear of another inadvertent dural puncture and choose the conservative management.

The other forms of therapy are strict bed rest for up to 7 days, hydration, caffeine, and epidural saline infusion. There are case reports of managing PDPH with administration of ACTH. There are a few case reports about use of SP ganglion block for PDPH but no prospective studies looking at onset, duration, side effects and long term follow up after Sphenopalatine ganglion block.

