2.3 Study Rationale

According to the Monro-Kellie hypothesis, within the confines of the cranium, the volume of CSF, blood and brain matter is kept in harmony. Changes in volume of any one will cause compensatory changes in one or both of the other.

A dural puncture causes loss of CSF and this is compensated for by an increase in cerebral blood flow (CBF) by vasodilatation, which in turn causes headache. This vasodilatation is mediated by parasympathetic inputs that synapse in the Sphenopalatine ganglion. Blockade of this ganglion would reduce parasympathetic activity and mitigate the headache.

SP ganglion block has been used to treat migraine and cluster headaches.

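### The complications endpoint, the per-patient safety review and follow-up to resolution cover only events attributed to the block or study drug, so a serious event judged unrelated is collected but can drop out of the complications result

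*Combined protocol and SAP*

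**What the plan says.** Three places in the combined protocol and SAP apply an attribution condition.

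- Section 1.3, secondary endpoint 1: "To monitor any complications due to SP ganglion block".
- Section 10.1: "Every patient will be reviewed for any harmful effects due to the SP ganglion block".
- Section 19.2: adverse events and test abnormalities "observed or reported to study team believed to be associated with the study drug(s) or device(s) will be followed until the event" has resolved or stabilised.

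Two further rules use similar filters. Section 19.5 sends to the IRB harms that are unexpected and probably related to the research procedures. The safety part of the stopping rule in 19.7 concerns morbidity caused by the procedure.

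Other text is wider. Section 19.1 defines an adverse event as "Any untoward medical occurrence associated with the use of the drug in humans, whether or not considered drug related". Section 19.2 opens by having all subjects questioned about adverse events, and 7.3 asks about new symptoms on Days 1, 2 and 7. Section 7.2.3 asks about residual headache or other symptoms at 1 month.

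On the condition itself, 2.1 says of headache after dural puncture that "if left untreated, it can lead to considerable morbidity including chronic neck and back pain, subdural hematoma, seizures and even death".

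**The concern.** The block is studied as a less invasive alternative to the epidural blood patch (12.2). Section 2.1 says the patch is intended to close the puncture. Section 2.3 gives the block a different action: "Blockade of this ganglion would reduce parasympathetic activity and mitigate the headache". A reader of the results will therefore want to know about procedural harms such as nasal bleeding, and also whether any treated subject had one of the serious events that 2.1 associates with the underlying condition.

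An investigator could reasonably judge a later subdural hematoma or seizure to come from the dural puncture and not from lidocaine or a swab. Under the wording of 1.3, 10.1 and 19.2, that judgement decides whether the event counts as a complication, whether it falls within the per-patient review, and whether it must be followed until it settles. With one open-label arm (7.1), there is no comparator against which to check the judgement.

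**Working it through.** The plan states no figure that depends on this point. The 30 subjects are a convenience sample (8.2), with no event rate, error rate or power. The main check is to trace one event through the text.

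**Tracing a subdural hematoma or seizure reported at a follow-up contact and judged to come from the puncture**

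1. Is it an adverse event? Yes. The definition in 19.1 does not depend on drug relation.
2. Would it be collected? Yes, if the subject reports it. The questioning in 19.2, 7.2.3 and 7.3 is not limited by cause, and 7.3 continues the calls even if the block fails.
3. Would it be assessed? Yes. Section 19.3 requires causality and seriousness to be determined for documented adverse events.
4. What follows from the causality finding? If it is unknown and of questionable relationship, 19.3 classes the event as associated, for reporting purposes. If it is unknown but not related, the finding and its rationale go into the subject's case history.
5. Does an event judged unrelated count under secondary endpoint 1? No. The endpoint requires that the block be the cause.
6. Does it fall within the review in 10.1? No, for the same reason. Section 10.2 only refers back to 10.1, so no wider data set is named for the cumulative review after every 5 patients (10.6).
7. Must it be followed until it resolves or stabilises? Not under 19.2, which ties that duty to believed association.
8. Does another outcome take it up? Not reliably. Secondary endpoint 3 reads "To monitor any residual effects at 1 months after the SP block" and does not define the effects. Sections 8.3 and 10.7 describe side effects, also undefined. None of them names hematoma or seizure.

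So the event passes collection and assessment (steps 1 to 3) and drops out at steps 5 to 7.

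**How often the gap could matter**

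Inputs: n = 30 (8.1). The event rate p per subject is an assumption, because the documents give none. Subjects are treated as independent.

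Formula: P(at least one event) = 1 − (1 − p)^30.

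- p = 0.1%: 1 − 0.999^30 = 0.030, or 3%
- p = 0.5%: 1 − 0.995^30 = 0.140, or 14%
- p = 1%: 1 − 0.99^30 = 0.260, or 26%
- p = 2%: 1 − 0.98^30 = 0.4545, or 45%
- p = 5%: 1 − 0.95^30 = 0.785, or 79%

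These are chances that an event occurs, not that it is left out. Omission also requires that it be judged unrelated.

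For scale, one omitted event would turn 1/30 = 3.3% into 0/30. Even a true 0/30 leaves a one-sided 95% upper bound of 1 − 0.05^(1/30) = 9.5%, so 30 subjects bound rare harms only loosely under any wording.

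**The case against.** The strongest reply is that the plan already collects harms regardless of cause. The definition in 19.1, the questioning in 19.2, the calls in 7.2.3 and 7.3 and the assessment in 19.3 all support it. This stands. A reader might infer that a hematoma or seizure would go unrecorded; the documents do not support that. The gap lies in what is counted and what must be followed.

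Second, uncertain events default to associated under 19.3. This also stands, but only for events of unknown and questionable relationship and only for reporting. An event judged unrelated is not reached.

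Third, the suspension criterion in 10.8 is not limited by attribution. That is correct, but it calls for a consistent trend, and a single serious event need not make one. Secondary endpoint 3 is likewise not worded causally, and the 1-month call asks about neck and back pain, so that part of the list in 2.1 is partly covered.

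Fourth, a reader might infer that the protocol itself attributes these harms to an unsealed dural leak that the block leaves in place. It does not. Section 2.1 speaks of headache after dural puncture left untreated, and 2.3 mentions loss of CSF without naming a harm from it. Continuing risk after pain relief is an inference. Conservative care, which is also an offered option (5.1.1.2), is not described as closing the puncture either.

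Fifth, the qualifier in 19.2 could be read as attached to abnormal test findings alone. Its natural reading covers adverse events too, and rewording would settle it.

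Finally, the Data Sheet and section 10.5 are not in the text available here. They may list specific events or add monitoring; nothing is inferred from their absence.

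**Conclusion.** The point holds in a limited form. Sections 1.3, 10.1 and 19.2 apply an attribution filter that the definition in 19.1 does not. A reported subdural hematoma or seizure would be recorded and assessed but, if judged unrelated to the block, would be outside the complications endpoint and outside the duty to follow to resolution. The complications result could then omit an event of a kind that 2.1 itself lists.

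Its size cannot be taken from the documents. Over assumed rates of 0.1% to 5%, the chance of at least one such event in 30 subjects runs from 3% to 79%. No rate in that range is supported over another, so the upper figures should not be read as an expectation. The conclusion rests on the wording and on the investigator judging the event unrelated, not on the rate.

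A reader might go further and infer that the study as a whole could report no harm. The documents do not support that, because the event would still be in the adverse-event record. Sample size, primary endpoints and error rates are unaffected. The change is worth making because it improves the safety conclusion and the follow-up of subjects with a serious event, and because these data are meant to inform a larger study (8.2).

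**What to change.** - In 1.3 (secondary endpoint 1), 8.3 and 10.1, count all adverse events from the block to the 1-month contact, with attribution to the block or study drug as a separate column. Block-attributed complications can still be read from that column.
- Tabulate the events named in 2.1 separately, whatever their attribution.
- In 19.2, follow every serious adverse event until it resolves or stabilises, regardless of attribution.

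This is a wording change. The planned contacts already ask about new or other symptoms, so it needs no added visit, no change in sample size and no change in treatment. The cost is that a few unrelated events will be listed and followed.
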